5.6. Exploratory Efficacy Analyses

5.6.1.

5.6.2.**6. SAFETY**

Unless otherwise stated, all safety analyses will be based upon the safety analysis set. No formal statistical comparison is planned.

Safety will be assessed by summarizing the incidence and type of AEs and examining changes in laboratory parameters (hematology and chemistry) and vital signs. There will be no imputation of missing values for clinical laboratory test results, vital sign measurements in the safety analyses.

In the safety analyses, subjects will be analyzed according to the treatment they actually received, regardless of the treatments they are randomized to. More specifically, if a subject only received one study agent, either golimumab or placebo, he/she will be analyzed under the treatment received. In rare situations of erroneous study agent switch, if a subject started to receive golimumab but with a wrong dose of placebo in the middle, the subject will be summarized in golimumab group. If a subject started to receive placebo but with a wrong dose of golimumab, the subject will be summarized under placebo until receiving golimumab and then under golimumab. The safety information of any subjects with wrong dosing will be listed.

6.1. Adverse Events

The verbatim terms used in the CRF by investigators to identify adverse events will be coded using the Medical Dictionary for Regulatory Activities (MedDRA). Any AE starting at or after the initial administration of study agent through the end of the trial is considered to be treatment emergent. If the event occurs on the day of the initial administration of study agent, and either event time or time of administration are missing, then the event will be assumed to be treatment emergent. If the event date is recorded as partial or completely missing, then the event will be

considered to be treatment emergent unless it is known to be prior to the first administration of study agent based on partial onset date or resolution date.

All reported treatment-emergent adverse events will be included in the analysis. Treatment-emergent adverse events (TEAEs) by system organ class and preferred term (ie, number and proportion of subjects with one or more TEAEs within a system organ class) will be summarized by treatment group.

The following TEAE summary tables will be provided:

- Any TEAEs
- TEAEs by severity
- Serious treatment-emergent adverse event (SAEs)
- Reasonably related TEAEs
- Frequent TEAEs
- TEAEs leading to study agent discontinuation
- Injection site reactions
- TEAEs of special interest such as hypoglycemia events, infections, tuberculosis, malignancies

These summary tables will provide the count and percentage of subjects with 1 or more of the specified AEs by treatment group, and by system-organ class/preferred term respectively.

In order to support the additional assessment of particular categories of adverse events, additional summary is done on selected adverse events. The number and percent of subjects with the following selected TEAEs will be summarized by treatment group:

In addition to the summary tables, listings of subjects with the following AEs will be provided:

- Death
- Serious TEAEs
- TEAEs leading to discontinuation of study agent
- Hypoglycemia episodes reported as TEAEs
- Key Safety findings including malignancies, opportunistic infections, a new autoimmune disease or worsening of an existing autoimmune disease, and so forth.

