Three data base locks (DBLs) are planned for the study. The first DBL will occur after all subjects complete their Week 52 assessments (double-blind period), the second DBL will occur after the last subject completes the off-therapy follow-up period (Week 104), and the third DBL will occur after the last subject completes the open-label extension period.

An interim analysis based on 4-hour C-peptide AUC in response to an MMTT is planned for the study after at least 60% of subjects complete their Week 26 MMTT assessment. The primary goal of this interim analysis is to obtain an early read on treatment effect to facilitate planning of future studies.

During the study, all subjects will receive intensive management of their diabetes with exogenous insulin according to the current recommendations of the American Diabetes Association (ADA). Subjects and, when applicable, their caregivers must agree to follow the current ADA recommendations of tight glycemic control with specific HbA1c targets. These current recommendations are intended to achieve glucose levels that appear to decrease some of the short- and long-term sequelae of T1D. This study will include adhering to the ADA's recommended glycemic control guidelines with an HbA1c target of <7.5% in children 17 years old and younger and <7% in those 18 years old and above.⁶⁷ Approaches to achieve these HbA1c goals will be the responsibility of the subject, their caregivers and their health care providers.

Responders at Week 52 who are still in the follow-up period and who are determined to be in the active treatment group will have the option to restart active therapy while the non-responders will continue to follow the originally planned study design, ie, the off-therapy follow-up monitoring period.

There will be an open-label extension period of the study for responders. Responders are defined as subjects who have profile at Week 52 which includes:

1. C-peptide and Remission score* responders (C+R responders): either having an increase in C-peptide AUC versus baseline or having a stable C-peptide AUC, ie, not decreasing more than 5% versus baseline and having a remission score ≤ 9 .

OR

2. C-peptide responders (C responders): either having an increase in C-peptide AUC versus baseline or having a stable C-peptide AUC, not decreasing more than 5% versus baseline but not meeting a remission score of ≤ 9 . Their remission score, however, must be <12.

OR

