9.2.3. Safety Endpoints

- Proportion of subjects with treatment-emergent AEs and severe AEs through Weeks 52 and 104.
- Proportion of subjects with study agent injection site reactions through Week 52.
- Proportion of subjects with severe infections through Weeks 52 and 104.

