11.9. Safety Endpoints and Analyses

Safety assessments will include the examination of the incidence rates of AEs, vital signs, laboratory parameters, and physical examinations. Safety analyses will be conducted on the safety analysis set, which is defined as all subjects who have received at least a 1 dose of study agent.

Adverse Events

The verbatim terms used in the CRF by investigators to identify AEs will be coded using the Medical Dictionary for Regulatory Activities (MedDRA). Treatment-emergent AEs are AEs with onset during the treatment period or that are a consequence of a pre-existing condition that has worsened since baseline. All reported treatment-emergent AEs will be included in the analysis. For each AE, the percentage of subjects who experience at least 1 occurrence of the given event will be summarized by system organ class and preferred term for treatment group. Treatment-emergent AEs will also be summarized by a maximum severity and relationship to study agent. Separate summaries will be provided for SAEs and AEs leading to study agent discontinuation.

In addition, summary tables will be presented by treatment group for each of the endpoints within each specified period:

Double-Blind Period:

- a. Proportion of subjects with treatment-emergent AEs and severe AEs through Weeks 52 and 104.
- b. Proportion of subjects with study agent injection site reactions through Week 52.
- c. Proportion of subjects with severe infections through Weeks 52 and 104.
- d. Open-Label Extension Period:
 1. Continue to evaluate safety and exploratory efficacy endpoints as per the [Time and Events Schedule](#) (open-label extension period) and no new efficacy hypotheses will be tested compared to the double-blind period.

Listings, datasets, or subject narratives may be provided, as appropriate, for those subjects who die, who discontinue treatment due to an AE, or who experience a severe or an SAE.

Clinical Laboratory Tests

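### SAP 6.1 sets no subject-level Week 52 window for its adverse event tables, so the Week 52 lock would not yield the protocol's through-Week-52 safety proportions

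*SAP*

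**What the plan says.** SAP 6.1 defines the treatment-emergent flag: "Any AE starting at or after the initial administration of study agent through the end of the trial is considered to be treatment emergent". It then says "All reported treatment-emergent adverse events will be included in the analysis". None of the AE tables listed there, including those for severity, infections and injection site reactions, carries a reporting window. SAP 1 limits the document to the Week 52 database lock.

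Protocol 11.9 defines the flag differently: "Treatment-emergent AEs are AEs with onset during the treatment period or that are a consequence of a pre-existing condition that has worsened since baseline". Protocol 9.2.3, repeated in 11.9, names the endpoints with their windows: "Proportion of subjects with treatment-emergent AEs and severe AEs through Weeks 52 and 104"; "Proportion of subjects with severe infections through Weeks 52 and 104"; and "Proportion of subjects with study agent injection site reactions through Week 52".

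On timing, Protocol 3.1 says "The first DBL will occur after all subjects complete their Week 52 assessments", and expects enrolment of the 81 subjects to take about 12 to 18 months. Treatment lasts 52 weeks, with the last dose given at the Week 52 visit (Protocol 9.1.3.3), followed by 52 weeks off therapy. AEs are collected throughout (Time and Events Schedule; Protocol 12.4.1).

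Elsewhere the SAP does write a Week 52 limit: disposition (4.2), compliance (4.3), hypoglycemia rate (5.4.2.2), laboratory summaries (6.2), pharmacokinetics (7.1) and pharmacodynamics (7.3).

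**The concern.** A lock date is not a cut-off for each subject. When the last subject reaches Week 52, those enrolled first will have been off therapy for up to a year, and their AEs from that time will be in the database. Under SAP 6.1 these events are treatment-emergent and are counted. Three things follow.

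- The percentages are not proportions through Week 52, which is the endpoint the protocol names.
- Subjects in one crude-percentage table have follow-up of unequal length, fixed by their enrolment date.
- If any excess risk on golimumab ends when treatment ends, time at background risk is added to both arms. Both percentages rise and the contrast between them shrinks. Infection matters most here, because Protocol 1.1 names serious infection as a known risk of the class and severe infection is a protocol endpoint.

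**Working it through.** The plan states no AE rate, so there is no figure of its own to reproduce. The check has two parts: how much off-therapy time enters the tables, and what that does to a proportion.

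**Off-therapy time at the lock.** Inputs: 52 weeks on and 52 weeks off therapy; enrolment over A = 52 or 78 weeks (12 or 18 months, Protocol 3.1). Assumptions: uniform entry, lock on the day the last subject reaches Week 52, no dropout. A subject who enters u weeks before the last one has min(u, 52) weeks off therapy.

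- A = 52: mean = 52/2 = 26.0 weeks; share of follow-up = 26.0/(52 + 26.0) = 33.3%.
- A = 78: mean = (52²/2 + 26 × 52)/78 = (1352 + 1352)/78 = 34.7 weeks; share = 34.7/86.7 = 40.0%. One third of subjects (26/78) would already have a full 52 weeks off therapy.
- With 8 weeks from last visit to lock, the shares become 39% and 43%.

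If the first 10 weeks after the last dose count as exposed (the interval of the post-treatment visit in Protocol 9.1.5.3), the unexposed time is max(min(u, 52) − 10, 0):

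- A = 52: (42²/2)/52 = 882/52 = 17.0 weeks; 17.0/78 = 22%.
- A = 78: (882 + 26 × 42)/78 = 1974/78 = 25.3 weeks; 25.3/86.7 = 29%.

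**Effect on a proportion.** Assume constant hazards, and the placebo hazard in both arms after Week 52. Let p_G and p_P be the true Week 52 proportions, and S the mean placebo probability of staying event-free over the added time. The tabulated proportions are 1 − (1 − p_G)S and 1 − (1 − p_P)S, so the difference becomes (p_G − p_P)S. For uniform entry over 52 weeks, S = p_P / [−ln(1 − p_P)]. For 78 weeks, S is two thirds of that value plus one third of (1 − p_P).

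| Assumed at Week 52 | Enrolment | S | Tabulated | Difference | Ratio |
|---|---|---|---|---|---|
| 60% vs 45% (15 points, ratio 1.33) | 12 months | 0.753 | 70% vs 59% | 11.3 points | 1.19 |
| 60% vs 45% | 18 months | 0.685 | 73% vs 62% | 10.3 points | 1.16 |
| 20% vs 10% (10 points, ratio 2.0) | 12 months | 0.949 | 24% vs 15% | 9.5 points | 1.65 |
| 20% vs 10% | 18 months | 0.933 | 25% vs 16% | 9.3 points | 1.58 |

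The absolute difference shrinks by the factor S, so it moves a good deal for common events and little for uncommon ones. For uncommon events it is the level and the ratio that change.

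**The case against.** The best defence is that a flag is not a table cut-off. The protocol wants treatment-emergent events through Week 104 as well. If only onset by Week 52 counted, that second endpoint would add almost nothing, so a flag that runs on is what makes it workable. The tension begins inside the protocol, between its definition in 11.9 and its endpoint in 9.2.3. The second limb of that definition, worsening of a pre-existing condition, has no treatment-period limit. SAP 1 ties the plan to the Week 52 lock, and the vital signs section (SAP 6.3) has no cut-off either. Part of this stands: counting off-therapy events is not wrong in itself. But SAP 6.1 does not merely stay silent. It gives the longer window and says that everything within it is included.

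Second, drug effect does not stop on the day of the Week 52 dose. Protocol 9.9 describes reactions 1 to 21 days after injection. This stands. It lowers the off-therapy share, and it rules out a hard cut at the Week 52 visit as the only analysis, because that would move reactions to the last dose into the off-therapy table.

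Third, consequences are limited. SAP 6 plans no formal safety comparison, and injection site reactions and events leading to discontinuation of study agent fall largely within treatment anyway. This also stands.

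A reader might infer that the plan would hide a sizeable infection excess. The documents do not support that. They give no AE rate, and if severe infections are uncommon, the absolute difference would hardly move under this model.

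**Conclusion.** The point holds as a missing reporting window. Followed as written, SAP 6.1 would put follow-up of unequal length into the Week 52 AE tables, and would not give the protocol's through-Week-52 proportions for treatment-emergent AEs, severe AEs and severe infections.

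Under uniform 12 to 18 month enrolment and no dropout, 33% to 40% of follow-up would be off therapy, or 22% to 29% with 10 weeks after the last dose counted as exposed. The direction of any distortion rests on the assumption that excess risk ends with treatment, and its size rests on assumed rates: a 15-point difference falls to 10 to 11 points at 60% vs 45%, and a 10-point difference to 9.3 to 9.5 at 20% vs 10%. No hypothesis test is affected. The change should be made, but the trial's conclusions on efficacy do not depend on it.

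**What to change.** In SAP 6.1:

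1. Keep the long-running treatment-emergent flag for the Week 104 endpoint, but state that the Week 52 AE tables count events with onset from first dose through each subject's Week 52 visit. Name the date that stands in where that visit was not made.
2. Add an on-treatment table that runs to last dose plus one prespecified lag, the same for completers and early stoppers, so that reactions to the Week 52 dose are kept.
3. Tabulate later off-therapy events separately, and report through Week 104 at the second lock.
4. Reconcile the protocol's definition in 11.9 with its Week 104 endpoint in 9.2.3, so that both documents use one definition.

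The cost is SAP wording, date filters and one extra set of tables. No new data are needed.

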6.2. Clinical Laboratory Tests

Clinical laboratory values are to be graded using National Cancer Institute Common Terminology Criteria for Adverse Events (NCI-CTCAE) version 4.03 (see [Table 4](#)). The laboratory data to be summarized are as follows:

Hematology Panel

-hemoglobin	-white blood cell (WBC) count with differential
-hematocrit	-platelet count

Serum Chemistry Panel

-sodium	-calcium
-potassium	-phosphate
-chloride	-albumin
-bicarbonate	-total protein
-blood urea nitrogen (BUN)	-total and direct bilirubin
-creatinine	-aspartate aminotransferase (AST)
-glucose	-alanine aminotransferase (ALT)
-alkaline phosphatase	

Additional Laboratory Tests

- C-reactive protein
- CD4 T-cell count
- CMV and EBV DNA PCR
- Lipids (cholesterol, HDL, LDL, Triglycerides)

The following clinical laboratory data analyses will be performed:

- Descriptive summary of the observed values and changes from baseline over time through Week 52.
- Descriptive summary of maximum NCI-CTCAE toxicity grade for postbaseline laboratory values through Week 52 for parameters listed in [Table](#) .
- Shift tables, using normal reference ranges, will also be presented for those laboratory parameters at each visit on which the laboratory tests are scheduled.
- Descriptive summary of maximum postbaseline measurement through Week 52 for ALT, AST and alkaline phosphatase and total bilirubin relative to ULN.
- Listings of subjects with any abnormal postbaseline laboratory values of CTCAE grade ≥ 2 will also be provided.

The baseline value for a subject is the value closest to but prior to the first dose of study agent (Week 0). Shift tables summarize the number of subjects with low, normal, and high values

(determined by the laboratory normal ranges) at the post baseline visit for each of the classifications of low, normal, and high at baseline.

Table 4: Grading Criteria for Clinical Laboratory Tests [CTCAE Version 4.03]

Hematology Tests		Criteria			
Test	Direction	1	2	3	4
Hemoglobin (g/L)	Decrease	≥ 100 - <LLN	≥ 80 - <100.0	≥ 65 - <80	<65
Neutrophils ($10^9/L$)	Decrease	≥ 1.5 - <LLN	≥ 1.0 - <1.5	≥ 0.5 - <1.0	<0.5
Platelets ($10^9/L$)	Decrease	≥ 75.0 - <LLN	≥ 50.0 - <75.0	≥ 25.0 - <50.0	<25.0
Total WBC count (Leukocytes $10^9/L$)	Decrease	≥ 3.0 - <LLN	≥ 2.0 - <3.0	≥ 1.0 - <2.0	<1.0
Lymphocytes ($10^9/L$)	Decrease	≥ 0.8 - <LLN	≥ 0.5 - <0.8	≥ 0.2 - <0.5	<0.2
Chemistry Tests		Criteria			
Test	Direction	1	2	3	4
ALT	Increase	>ULN - ≤ 3.0 xULN	>3.0 xULN - ≤ 5.0 xULN	>5.0 xULN - ≤ 20.0 xULN	>20.0 xULN
AST	Increase	>ULN - ≤ 3.0 xULN	>3.0 xULN - ≤ 5.0 xULN	>5.0 xULN - ≤ 20.0 xULN	>20.0 xULN
Albumin (g/L)	Decrease	≥ 30 - <LLN	≥ 20 - <30	<20	
Alkaline Phosphatase	Increase	>ULN - ≤ 2.5 xULN	>2.5 xULN - ≤ 5.0 xULN	>5.0 xULN - ≤ 20.0 xULN	>20.0 xULN
Bilirubin (total)	Increase	>ULN - ≤ 1.5 xULN	>1.5 xULN - ≤ 3.0 xULN	>3.0 xULN - ≤ 10.0 xULN	>10.0 xULN
Calcium (mmol/L)	Increase	>ULN - ≤ 2.9	>2.9 - ≤ 3.1	>3.1 - ≤ 3.4	>3.4
Calcium (mmol/L)	Decrease	[Albumin ≥ 40 g/L or missing and calcium ≥ 2.0 - <LLN]; or [Albumin < 40 g/L and (calcium - 0.8 x (albumin - 40)) ≥ 2.0 - <LLN]	[Albumin ≥ 40 g/L or missing and calcium ≥ 1.75 - <2.0]; or [Albumin < 40 g/L and (calcium - 0.8 x (albumin - 40)) ≥ 1.75 - <2.0]	[Albumin ≥ 40 g/L or missing and calcium ≥ 1.5 - <1.75]; or [Albumin < 40 g/L and (calcium - 0.8 x (albumin - 40)) ≥ 1.5 - <1.75]	[Albumin ≥ 40 g/L or missing and calcium <1.5]; or [Albumin < 40 g/L and (calcium - 0.8 x (albumin - 40)) <1.5]
Creatinine	Increase	>ULN - ≤ 1.5 xULN	>1.5 xULN - ≤ 3.0 xULN	>3.0 xULN - ≤ 6.0 xULN	>6.0 xULN
Phosphate (mmol/L)	Increase	>ULN - ≤ 5.5	>5.5 - ≤ 6.0	>6.0 - ≤ 7.0	>7.0
Phosphate (mmol/L)	Decrease	≥ 0.8 - <LLN	≥ 0.6 - <0.8	≥ 0.3 - <0.6	<0.3
Potassium (mmol/L)	Increase	>ULN - ≤ 5.5	>5.5 - ≤ 6.0	>6.0 - ≤ 7.0	>7.0
Potassium (mmol/L)	Decrease	≥ 3.0 - <LLN		≥ 2.5 - <3.0	<2.5
Sodium (mmol/L)	Increase	>ULN - ≤ 150	>150 - ≤ 155	>155 - ≤ 160	>160
Sodium (mmol/L)	Decrease	≥ 130 - <LLN		≥ 120 - <130	<120

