- C-reactive protein
- CD4 T-cell count
- CD8 T-cell count
- HIV antibody - only at screening
- hepatitis B antibody/antigen panel - only at screening
- hepatitis C virus antibody - only at screening
- CMV and EBV DNA PCR
- MHC haplotype – only at Week 0 (randomization)
- Lipids (cholesterol, HDL, LDL, Triglycerides) – Only done at fasting visits: screening, Week 12, 26, 38, 52, 78 and 104.
- Coagulation panel (PT/PTT/INR) - only at screening
- Serum pregnancy testing - only at screening (for females of childbearing potential)

The following test will be performed at the study site:

- Urine pregnancy testing (for females of childbearing potential)

During the study, all abnormal laboratory values will require further explanation from the investigator. Clinically significant abnormal laboratory values should be repeated until they return to normal or are otherwise explained by the investigator.

Clinical Assessments:

Vital Signs (oral or tympanic temperature, pulse/heart rate, respiratory rate, blood pressure)

Blood pressure and pulse/heart rate measurements can be assessed with a completely automated device. Manual techniques will be used if an automated device is not available. Blood pressure and pulse/heart rate measurements should be preceded by at least 5 minutes of rest in a quiet setting without distractions (eg, television, cell phones).

Physical Examination

Physical examinations (PE; full or brief) sometimes including height and body weight will be conducted at times indicated in the [Time and Events Schedule](#).

A full physical exam includes an evaluation of general appearance, head, eyes, ears, nose, and throat evaluation, neck palpation for thyroid, lymphadenopathy and tenderness, auscultation of the heart, lungs and abdomen, palpation of abdomen, external evaluation of genitalia with Tanner Staging, evaluation of extremities and skin, and gross neurologic evaluation of strength, sensation and balance.

A brief physical examination includes general appearance, head, eyes, and throat evaluation, neck palpation for thyroid, lymphadenopathy and tenderness, auscultation of the heart, lungs and abdomen, palpation of abdomen, evaluation of extremities and skin.

Any clinically relevant finding or change in physical exam occurring during the study must be recorded on the Adverse Event section of the CRF.

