Laboratory data will be summarized by type of laboratory test. Reference ranges and markedly abnormal results (specified in the SAP) will be used in the summary of laboratory data. Descriptive statistics will be calculated for each laboratory analyte at baseline and for observed values and changes from baseline at each scheduled timepoint. Frequency tabulations of the changes from baseline will be presented in pre- versus post-treatment cross-tabulations (with classes for below, within, and above normal ranges). Frequency tabulations of the abnormalities will be made. A listing of subjects with any markedly abnormal laboratory results will be provided.

Vital Signs

Descriptive statistics of temperature, pulse/heart rate, respiratory rate, and blood pressure (systolic and diastolic) values and changes from baseline will be summarized at each scheduled timepoint. The percentage of subjects with values beyond clinically important limits will be summarized and a corresponding listing will be provided.

Physical Examination

Proportion of subjects with abnormal physical examination findings will be summarized at each scheduled timepoint. Subjects with any post-treatment abnormalities will be listed.

Open-Label Extension Period

Clinical laboratory tests, vital signs, and physical examination for the open-label extension period will be assessed as similar to the double-blind period.

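### SAP Table 4 adjusts calcium in mmol/L for albumin in g/L with a coefficient of 0.8, so low calcium escapes grade 2 or higher once albumin falls a little below 40 g/L

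*SAP*

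**What the plan says.** SAP section 6.2 grades laboratory values with Table 4. The calcium row label begins "Calcium (mmol/L", and albumin is given in g/L. For a calcium decrease, raw calcium is graded when albumin is at least 40 g/L or missing. Otherwise the graded quantity is an adjusted calcium, defined by "Albumin < 40 g/L and (calcium - 0.8 x (albumin - 40" with the brackets then closed. This term appears in the cells for grades 1, 2, 3 and 4. The limits are:

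- grade 1: 2.0 up to the lower limit of normal
- grade 2: 1.75 to below 2.0
- grade 3: 1.5 to below 1.75
- grade 4: below 1.5 mmol/L

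No source is given for 0.8.

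Two planned outputs use these grades. One is the "Descriptive summary of maximum NCI-CTCAE toxicity grade for postbaseline laboratory values through Week 52". The other is "Listings of subjects with any abnormal postbaseline laboratory values of CTCAE grade" 2 or above. A third output does not use them: "Shift tables, using normal reference ranges, will also be presented for those laboratory parameters at each visit" with scheduled tests.

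Protocol section 11.9 says "Reference ranges and markedly abnormal results (specified in the SAP) will be used in the summary of laboratory data" and adds "A listing of subjects with any markedly abnormal laboratory results will be provided". Protocol section 9.6 says "During the study, all abnormal laboratory values will require further explanation from the investigator".

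**The concern.** The coefficient does not fit the units beside it. An albumin adjustment should move calcium modestly relative to the grade bands. Here a change of 1 g/L in albumin moves calcium by more than the whole distance from grade 4 to the edge of grade 1.

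The error runs one way. Below 40 g/L the rule can only raise the graded calcium, so it can only lower the grade or leave it as it was. A subject with markedly low calcium and slightly reduced albumin would appear with grade 1 or no grade in the maximum-grade summary and would be absent from the listing. That listing is the only subject-level laboratory listing that SAP 6.2 names.

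**Working it through.** **Inputs.** All are from SAP Table 4: calcium in mmol/L, albumin in g/L, coefficient 0.8, reference albumin 40, and grade limits 2.0, 1.75 and 1.5 mmol/L. The table's highest calcium limit is 3.4 mmol/L (grade 4 increase), and grade 1 for low albumin runs down to 30 g/L. The lower limit of normal for calcium is not given, but results for grade 2 or higher do not depend on it.

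**Rule as printed.** For albumin below 40:

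adjusted Ca = Ca + 0.8 × (40 − albumin)

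**Size per unit of albumin.** A fall of 1 g/L adds 0.8 mmol/L. The bands are 0.25 mmol/L wide, so this is 0.8/0.25 = 3.2 bands. From the grade 4 limit to the top of grade 2 is 2.0 − 1.5 = 0.5 mmol/L.

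**Where a value leaves the listing.** Grade 2 or higher needs adjusted Ca below 2.0, so a value drops out at albumin = 40 − (2.0 − Ca)/0.8 or lower.

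| Raw Ca (mmol/L) | Grade at albumin 40 | Leaves the listing at albumin (g/L) or lower |
|---|---|---|
| 1.9 | 2 | 40 − 0.1/0.8 = 39.875 |
| 1.6 | 3 | 40 − 0.4/0.8 = 39.5 |
| 1.4 | 4 | 40 − 0.6/0.8 = 39.25 |
| 0 | 4 | 40 − 2.0/0.8 = 37.5 |

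The last row shows that at 37.5 g/L or lower no positive calcium value can be grade 2 or higher.

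**One value followed down (Ca 1.4).**

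- Albumin 39.9: 1.4 + 0.08 = 1.48, still grade 4.
- Albumin 39.5: 1.4 + 0.40 = 1.80, grade 2.
- Albumin 39: 1.4 + 0.80 = 2.20, at most grade 1.
- Albumin 35: 1.4 + 4.0 = 5.4, no low-calcium grade under any plausible lower limit of normal.

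**Plausibility within the same table.** At albumin 30 g/L the rule adds 0.8 × 10 = 8.0 mmol/L, which exceeds the highest calcium limit in the table (3.4). The added amount alone reaches 3.4 at albumin 40 − 3.4/0.8 = 35.75.

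**A coefficient in the table's units.** The documents do not say where 0.8 comes from. Assume it is a slope in mg/dL of calcium per g/dL of albumin, with a molar mass of 40.08 for calcium. Then 0.8 mg/dL = 0.8 × 10/40.08 ≈ 0.20 mmol/L per g/dL, or 0.20/10 ≈ 0.020 mmol/L per g/L. The printed value is about 40 times larger (32 to 53 times for an assumed range of 0.025 to 0.015).

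With 0.02, the three exit points become:

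- Ca 1.9: 40 − 0.1/0.02 = 35 g/L
- Ca 1.6: 40 − 0.4/0.02 = 20 g/L
- Ca 1.4: 40 − 0.6/0.02 = 10 g/L

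Ca 1.4 at albumin 35 becomes 1.4 + 0.02 × 5 = 1.50 (1.475 to 1.525 over the range). That is grade 3 or 4, so the subject stays listed.

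**The case against.** The strongest reply is that little may follow in practice. An output changes only when calcium below 2.0 mmol/L and albumin below 40 g/L occur in the same sample. The documents give no distribution for either, so the count among about 81 subjects is unknown and could be zero. Calcium is not an endpoint and is not a named stopping criterion, and SAP section 6 plans no formal safety comparison. Observed-value summaries and shift tables would still show low values. Protocol 9.6 also requires clinically relevant laboratory changes to be recorded as adverse events, which gives a second reporting route. All of this stands, and it limits the severity.

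Three narrower points also stand:

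- The loss is gradual. As printed, calcium below 1.60 at albumin 39.5, or below 1.20 at albumin 39, still reaches grade 2 or higher.
- Any albumin adjustment removes some values by design. Even with 0.02, calcium 1.9 leaves the listing at albumin 35.
- The comparison with 3.4 mmol/L shows only that the adjusted values are implausible. The calcium-increase row has no albumin term, so no false high-calcium grade arises.

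The tie to protocol 11.9 is an inference. SAP 6.2 does not call grade 2 or higher markedly abnormal, and the SAP uses that term only for vital signs in section 6.3. The grade-based listing is, however, the only one in 6.2 that could meet the protocol's commitment.

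None of this makes the rule usable. Shift tables give counts of low, normal and high; they neither grade severity nor identify subjects. A programmer might notice the error, but a prespecified rule should not depend on that.

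**Conclusion.** The concern holds. The unit mismatch is printed in all four cells, and no other text corrects it. Its effect follows from the table's own limits without any outside source. By albumin 39.375 g/L (40 − 0.5/0.8), every raw calcium value from 1.5 to below 2.0 mmol/L has left the listing. At 37.5 g/L or lower, grades 2 to 4 are unattainable.

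The damage is confined to the maximum-grade summary and the grade 2 or higher listing, both descriptive, and only if the rule is programmed as written. How many subjects would be affected cannot be told from the documents. The defect itself rests on no assumption; only the replacement value of about 0.02 does. This should be corrected before the Week 52 outputs are programmed, but it does not threaten the trial's conclusions on efficacy.

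**What to change.** State the source of the albumin adjustment and express its coefficient in mmol/L per g/L in all four calcium-decrease cells of SAP Table 4. If the source confirms that 0.8 is in mg/dL per g/dL, the value is about 0.02. Alternatively, keep 0.8, give calcium and albumin in the units it belongs to, and convert the grade limits.

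As a query only: the phosphate-increase limits (5.5, 6.0 and 7.0 mmol/L) are identical to the potassium-increase limits in all four grades. The sponsor should check that row against the grading version the SAP cites.

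The cost is one coefficient in four cells and one row to verify, with no new data and no new analysis.

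### SAP Table 4 grades high phosphate with the same cut-offs as high potassium (5.5/6.0/7.0 mmol/L), out of scale with phosphate's own low-side bands; check the row against the cited scale and correct it

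*SAP*

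**What the plan says.** SAP section 6.2 grades laboratory values by NCI-CTCAE version 4.03 and sets out the bands in Table 4. The high-phosphate row opens with "Phosphate (mmol/L) Increase >ULN". Its grade 1 is "Phosphate (mmol/L) Increase >ULN - ≤ 5.5", and grades 2 to 4 follow as ">5.5 - ≤ 6.0 >6.0 - ≤ 7.0 >7.0". For high potassium, grade 1 is "Potassium (mmol/L) Increase >ULN - ≤ 5.5", and the next three bands are again 5.5 to 6.0, 6.0 to 7.0 and above 7.0 mmol/L. The low-phosphate row starts at "Phosphate (mmol/L) Decrease ≥ 0.8 - <LLN" and steps down through 0.6 and 0.3 mmol/L.

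Section 6.2 puts the grades to two uses. One is a summary of the maximum post-baseline grade through Week 52. The other is stated as "Listings of subjects with any abnormal postbaseline laboratory values of CTCAE grade ≥ 2 will also be provided".

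The section also plans descriptive summaries of observed values and changes over time, and shift tables of low, normal and high. A further summary gives the maximum post-baseline value relative to ULN, but only for ALT, AST, alkaline phosphatase and total bilirubin. Protocol section 11.9 calls for a listing of subjects with markedly abnormal laboratory results and leaves the definition to the SAP.

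**The concern.** Two analytes with different low-side scales share identical high-side bands, and neither document explains why. The likeliest reason is that the potassium cells were copied into the phosphate row.

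A programmer would implement the row as printed. Phosphate values well above normal would then be reported as grade 1, and those subjects would be missing from the grade-based listing. Table 4 is the only graded laboratory specification in the SAP, so that listing reads as the SAP's answer to the protocol's commitment on markedly abnormal results. At stake is the accuracy of two descriptive safety outputs for one analyte in one direction.

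**Working it through.** No sample-size, power or alpha figure is involved. The check has three steps.

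**1. The two rows side by side (SAP Table 4, mmol/L).**

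| Row | Grade 1 | Grade 2 | Grade 3 | Grade 4 |
|---|---|---|---|---|
| Phosphate, increase | >ULN to 5.5 | >5.5 to 6.0 | >6.0 to 7.0 | >7.0 |
| Potassium, increase | >ULN to 5.5 | >5.5 to 6.0 | >6.0 to 7.0 | >7.0 |
| Phosphate, decrease | 0.8 to <LLN | 0.6 to <0.8 | 0.3 to <0.6 | <0.3 |
| Potassium, decrease | 3.0 to <LLN | (blank) | 2.5 to <3.0 | <2.5 |

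All four increase bands match, in the same unit. The decrease bands do not.

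**2. Is the phosphate row out of pattern within the table?** For each electrolyte graded in both directions by fixed limits, divide the upper limit of grade 1 high by the lower limit of grade 1 low:

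- Sodium: 150/130 = 1.15
- Calcium: 2.9/2.0 = 1.45
- Potassium: 5.5/3.0 = 1.83
- Phosphate: 5.5/0.8 = 6.88, or about 6.9

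Phosphate is the outlier, and the numerator that makes it so is potassium's. The ratio shows that the row is out of pattern. It does not measure how many values would be misgraded.

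**3. What the row does as printed.** A value above ULN is grade 1 up to and including 5.5. A value of 5.51 is grade 2, 6.01 is grade 3 and 7.01 is grade 4. So no phosphate above ULN and up to 5.5 mmol/L can reach the grade 2 listing.

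Neither document gives a phosphate ULN, so the multiple of ULN at which grade 2 begins has to be shown over an assumed range. The formula is 5.5 / ULN:

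| Assumed ULN (mmol/L) | Grade 2 starts above |
|---|---|
| 1.4 | 5.5/1.4 = 3.93 × ULN |
| 1.5 | 5.5/1.5 = 3.67 × ULN |
| 1.8 | 5.5/1.8 = 3.06 × ULN |
| 2.0 | 5.5/2.0 = 2.75 × ULN |

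The ULN values are illustrative assumptions. The finding that the two rows are identical does not depend on them.

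**The case against.** The strongest reply is that little is lost. Protocol section 11.9 and SAP section 6.2 both require by-visit summaries of observed values and changes, and protocol section 11 names minimum and maximum among its example statistics, so the degree of any elevation would probably be visible by arm. Shift tables would show movement from normal to high. Protocol section 9.6 has investigators review laboratory results and record clinically relevant changes as adverse events, and SAP section 6.1 tabulates those by severity. SAP section 6 plans no formal safety comparison, and no discontinuation criterion in protocol section 10.2 names phosphate.

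All of this stands, and it sets the size of the point. It does not restore what the row removes: shift tables give no degree, by-visit summaries do not identify subjects, and the summary relative to ULN omits phosphate.

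It can also be said that the ratio comparison is circumstantial and that copying is inferred. That is fair. Neither document says the row was copied, and neither reproduces CTCAE 4.03, so the right bands cannot be stated from them.

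A reader might go further and infer that every realistic high phosphate would be grade 1, or that the table would show no relevant elevation whatever the data. The documents do not support either statement. Both need a ULN and an expected range that are not given, and a value above 5.5 mmol/L would still be graded 2 to 4 and listed.

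**Conclusion.** The point holds in a limited form. The phosphate-increase bands are identical to potassium's and do not fit phosphate's own decrease bands, with a high-to-low ratio of 6.9 against 1.15 to 1.83 for the other three electrolytes. As written, phosphate above ULN and up to 5.5 mmol/L is grade 1 and stays out of the listing. If the ULN lies between 1.4 and 2.0 mmol/L, that covers elevations up to about 3.9 to 2.75 times ULN.

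The loss is grade separation and subject-level listing for one analyte in one direction. No efficacy result, power or alpha is touched. That the row was copied is the natural inference, but it remains an inference. Severity: minor correction.

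**What to change.** Check the phosphate-increase row against CTCAE version 4.03, the scale that Table 4 cites, and replace it with the phosphate-specific cut-offs given there. If that scale has no grade for high phosphate, delete the row and add phosphate to the existing SAP 6.2 summary of the maximum post-baseline value relative to ULN. If a subject listing is wanted on that basis, the sponsor should set its threshold in advance, because the present summary names none.

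The cost is one table row and the matching program specification. No data collection changes.
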